1.1. Study Objectives

The purpose of the RDN-CKD Study is to demonstrate the ability of the ReCor catheter system to effectively reduce systolic and diastolic ambulatory BP in hypertensive subjects with uncontrolled hypertension and CKD stage 3. The objective of the RDN-CKD Study is to demonstrate the efficacy and verify the safety of RDN in hypertensive subjects with CKD stage 3. Patients included in this study are hypertensive despite of receiving 1-5 antihypertensive drug classes.

1.1.1. Primary objective

The primary efficacy parameter is:

- Change in systolic 24-h ambulatory BP at 6 months post-RDN-procedure from pre-procedure (including 1. Pre-treatment value (**P**) = average of the pre-procedure visit (week -1) value and screening visit (week -4) value, 2. Baseline value (**B**) = pre-procedure visit (week -1) value only) compared *between the 2 groups* (RDN-Treatment group vs. Sham group).

1.1.2. Secondary objectives

The secondary efficacy parameters of the study are (*between the 2 groups* - RDN-Treatment group vs. Sham group):

- Change in systolic 24-h ambulatory BP at 3 and 12 months post-procedure from pre-procedure (including P and B) compared between the 2 groups (RDN-Treatment group vs. Sham group).
- Change in diastolic 24-h ambulatory BP at 3, 6 and 12 months post-procedure from pre-procedure (including P and B) compared between the 2 groups (RDN-Treatment group vs. Sham group).
- Change in office systolic and diastolic BP at 3, 6 and 12 months post-procedure from pre-procedure (including P and B) compared between the 2 groups (RDN-Treatment group vs. Sham group).
- Change in home systolic and diastolic BP at 3, 6 and 12 months post-procedure from pre-procedure (including B only) compared between the 2 groups (RDN-Treatment group vs. Sham group).
- Responder rate in BP (systolic office BP ≥ 10 mmHg, or 24-h systolic ambulatory BP ≥ 5

mmHg) at 3, 6, and 12 months post-procedure from pre-procedure (including P and B) compared between the 2 groups (RDN-Treatment group vs. Sham group).

- Change in serum creatinine, cystatin C at all time points from pre-procedure (pre-procedure visit (week -1) value and screening visit (week -4)) compared between the 2 groups (RDN-Treatment group vs. Sham group).
- Change in eGFR (calculated based on CKD-epi formula) derived from serum creatinine at all time points from pre-procedure (pre-procedure visit (week -1) value and screening visit (week -4)) compared between the 2 groups (RDN-Treatment group vs. Sham group). [1]
- Change in eGFR derived from cystatin C at all time points from pre-procedure (pre-procedure visit (week -1) value and screening visit (week -4)) compared between the 2 groups (RDN-Treatment group vs. Sham group). [2, 3]
- Change in eGFR derived from creatinine/Cystatin-C formula at all time points from pre-procedure (pre-procedure visit (week -1) value and screening visit (week -4)) compared between the 2 groups (RDN-Treatment group vs. Sham group) [3]
- Change of the slope of eGFR (derived from creatinine; CKD-epi formula) after half year and one year post-procedure from pre-procedure (pre-procedure visit (week -1) value and screening visit (week -4) eGFR values) compared between the 2 groups (RDN-Treatment group vs. Sham group).
- Change of the slope of eGFR (derived from creatinine; CKD-epi formula) after half year and at 1 year post-procedure from pre-procedure (pre-procedure visit (week -1) value and screening visit (week -4) eGFR values) compared to the historical slope the year before
- Change in proteinuria (per g urinary creatinine), albuminuria (per g urinary creatinine), urine sodium (per g urinary creatinine), urine potassium (per urinary creatinine), urine creatinine concentration at 3, 6 and 12 months post-procedure from pre-procedure (pre-procedure visit (week -1) value and screening visit (week -4)) compared between the 2 groups (RDN-Treatment group vs. Sham group). Win ratio analysis will be conducted, with the criteria 24h ambulatory systolic BP change > 5 mmHg, and office systolic BP change > 10 mmHg at 3, 6 and 12 months from pre-procedure (including P and B) in both groups (RDN-Treatment group vs. Sham group). [4]
- Win ratio analysis will be conducted, with the criteria 24h ambulatory systolic BP change > 5 mmHg, office systolic BP change > 10 mmHg, and decrease of medication number at 3, 6 and 12 months from pre-procedure (including P and B) in both groups (RDN-Treatment group vs. Sham group). [4]
- Win ratio analysis will be conducted, with the criteria 24h ambulatory systolic BP change > 5 mmHg, office systolic BP change > 10 mmHg, and any decrease of drug burden index in both groups at 3, 6 and 12 months from pre-procedure (including P and B) in both groups

(RDN-Treatment group vs. Sham group). [4]

- Win ratio analysis will be conducted, with the criteria 24h ambulatory systolic BP change > 5 mmHg, office systolic BP change > 10 mmHg, and any decrease of antihypertensive load index at 3, 6 and 12 months from pre-procedure (including P and B) in both groups (RDN-Treatment group vs. Sham group). [4]

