- Change of the slope of eGFR (derived from creatinine; CKD-epi formula) after half year and one year post-procedure from pre-procedure (pre-procedure visit (week -1) value and

screening visit (week -4) eGFR values) compared between the 2 groups (RDN-Treatment group vs. Sham group).

- Change of the slope of eGFR (derived from creatinine; CKD-epi formula) after half year and at 1 year post-procedure from pre-procedure (pre-procedure visit (week -1) value and screening visit (week -4) eGFR values) compared to the historical slope the year before
- Change in proteinuria (per g urinary creatinine), albuminuria (per g urinary creatinine), urine sodium (per g urinary creatinine), urine potassium (per urinary creatinine), urine creatinine concentration at 3, 6 and 12 months post-procedure from pre-procedure (pre-procedure visit (week -1) value and screening visit (week -4)) compared between the 2 groups (RDN-Treatment group vs. Sham group). Win ratio analysis will be conducted, with the criteria 24h ambulatory systolic BP change > 5 mmHg, and office systolic BP change > 10 mmHg at 3, 6 and 12 months from pre-procedure (including P and B) in both groups (RDN-Treatment group vs. Sham group). [4]
- Win ratio analysis will be conducted, with the criteria 24h ambulatory systolic BP change > 5 mmHg, office systolic BP change > 10 mmHg, and decrease of medication number at 3, 6 and 12 months from pre-procedure (including P and B) in both groups (RDN-Treatment group vs. Sham group). [4]
- Win ratio analysis will be conducted, with the criteria 24h ambulatory systolic BP change > 5 mmHg, office systolic BP change > 10 mmHg, and any decrease of drug burden index in both groups at 3, 6 and 12 months from pre-procedure (including P and B) in both groups (RDN-Treatment group vs. Sham group). [4]
- Win ratio analysis will be conducted, with the criteria 24h ambulatory systolic BP change > 5 mmHg, office systolic BP change > 10 mmHg, and any decrease of antihypertensive load index at 3, 6 and 12 months from pre-procedure (including P and B) in both groups (RDN-Treatment group vs. Sham group). [4]

Other Observational Efficacy Assessments:

- Change in average daytime/night-time ambulatory systolic BP at 3, 6 and 12 months post-procedure from pre-procedure (including P and B) compared between the 2 groups (RDN-Treatment group vs. Sham group).

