2.4. Analyses

Statistical analyses will be based on the basis of international guidelines (CPMP/ICH/363/96:E9). Due to the early stop of the study, only an exploratory and descriptive analysis takes place. Statistical methods used to compare groups for primary and secondary outcomes:

Efficacy: Change of systolic 24-h ambulatory BP at 6 months post-procedure (primary efficacy endpoint) compared between the RDN and sham group will be analyzed in a linear mixed model including the covariates that were significantly different between the groups at baseline. All secondary (see 1.1.2) and observational endpoints (1.1.3 and 1.1.4) are analyzed also via a modelling approach adjusting for potential imbalances in baseline characteristics. The type I error for the analysis of the primary endpoint is set at 5% (two-sided), all analyses of secondary endpoints have an exploratory character avoiding multiplicity issues in this trial.

In addition, a win ratio analysis will be conducted, with the criteria 24h ambulatory systolic BP change > 5 mmHg, office systolic BP change > 10 mmHg, and decrease of medication as defined by following 3 parameters (number of antihypertensive drugs, drug burden index and antihypertensive load index).

Analysis will be performed for the following populations:

1. Primary analysis is based on *the intention-to-treat* (ITT) population consisting of all randomized study subjects that are all either RDN treated or sham treated.
2. A secondary analysis will be done with a *modified ITT* population (mITT) in which participants with adherence violations will be excluded (sensitivity analyses).
3. A secondary analysis will be done with the *per protocol population* (PPP) in which study subjects with predefined protocol deviations (defined prior to unblinding of the data) are excluded.
4. A secondary analysis will be done with the modified *per protocol population* (mPPP) in which study subjects of the PPP with adherence violation are excluded.
5. A secondary analysis will be done with the safety population (SAF) in which all study subjects signing informed consent are included.

6. A secondary analysis will be done with those patients that are investigated by the Erlanger and Nürnberger center (CRC staff), with a total of N=20 randomized patients (Bavarian cohort)

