- Resolved
- Resolved with sequelae
- Ongoing
- Death

Recording and Reporting of Adverse Events

The period of observation for AEs extends from Study Screening/Baseline Eligibility Visit 1 (Week -4) until Visit 10 (Week +52). New AEs reported to the investigator during the observational period, after the study procedure must be documented, treated, and followed up like all other AEs.

AEs will not be followed up after the final investigation visit which is scheduled 12 months after the treatment with the investigational medical device.

Underlying diseases/pre-existing conditions that do not worsen during the course of the investigation are not reportable as AEs. To determine whether a condition has worsened, it is compared to the condition of the subject at baseline.

Elective treatments planned before screening and which are documented in the subject's source data are usually not regarded as AEs.

Data pertaining to AEs will be collected during each investigation visit based through the investigators inquiry or discovered in the course of examinations done during the visit. The investigators will assess and record any AE in detail in the subject file and on the CRF AE report form.

The following information were recorded:

- AE diagnosis or main symptom.
- Date of event onset.
- Severity
- Investigational medical device (blinded)
- Causal relationship (causal related, probably related, possibly related, unlikely related, not related).
- Serious (yes or no).
- Patient outcome
- Action taken /treatment.
- AE falling under the definition of an AESI (yes or no)
- AE leading to discontinuation of the investigation (yes or no)
- AE due to a device deficiency (yes/no)
- Date of event resolution

After completion of all scheduled visit assessments the investigator must document any AEs arising from these assessments. In case of an SAE, the investigator must also complete an SAE report form.

Recording and Reporting of Serious Adverse Events

All SAEs that occur during the investigation period, whether considered to be related to the investigational medical device/procedures or not, were reported by the investigator to the Sponsor within 24 hours of knowledge.

SAE report forms are provided in the ISF. Completed reports were signed by an investigator and transferred by fax to:

Medical Device Vigilance Office
Center for Clinical Studies (CCS Erlangen)
Universitätsklinikum Erlangen
[name]

[name]
[contact]
email: [contact]

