2.9.5.2. Criteria for clinically notable laboratory abnormalities

Please note: Normal ranges are given by the central laboratory of the University Hospital Erlangen-Nuremberg

Liver parameters:

Serum SGOT, SGPT, γ -GT, AP > 30% of upper normal range

Renal parameters:

decrease of eGFR (CKD-Epi) >30%, serum potassium above normal range, serum sodium under normal range

Hematological parameters:

Abnormal blood cell counts at baseline and changes of $\geq 20\%$ of blood cell counts

Descriptive statistics of all laboratory values will be given.

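### Three of the four exploratory win ratios credit any reduction of antihypertensive medication as a win whatever its cause, so a drug stopped for a renal or potassium finding counts as efficacy

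*SAP*

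**What the plan says.** SAP sections 1.1.2 and 2.1 plan four win ratios at 3, 6 and 12 months. The first uses BP alone: "24h ambulatory systolic BP change > 5 mmHg, and office systolic BP change > 10 mmHg at 3, 6 and 12 months". The other three each add one medication criterion:

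- number of drugs: "office systolic BP change > 10 mmHg, and decrease of medication number at 3, 6 and 12 months from pre-procedure"
- drug burden index: "and any decrease of drug burden index in both groups at 3, 6 and 12 months from pre-procedure"
- antihypertensive load index: "and any decrease of antihypertensive load index at 3, 6 and 12 months from pre-procedure"

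Section 2.4 summarises the component as "decrease of medication as defined by following 3 parameters" and adds no rule on why the medication fell. Section 1.1.3 also lists the change in drug number and in both indices as observational endpoints, again without regard to reason.

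The same document treats renal and potassium changes as safety matters. Section 1.1.5 lists acute renal injury, defined partly by a creatinine rise or eGFR fall, among the adverse events of special interest. Section 2.9.5.2 flags "decrease of eGFR (CKD-Epi) >30%, serum potassium above normal range" as clinically notable.

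**The concern.** A lower drug count is taken as evidence that less treatment was needed. In CKD stage 3 a drug can also be reduced because of a renal or potassium finding. Under the planned scoring, such a patient who ties with an opponent on both BP criteria beats that opponent if the opponent's medication was not reduced. One event can then appear as a safety finding and, through the drug it stops, as an efficacy win. If these reductions are more frequent in one arm, the medication criterion favours that arm for a reason unrelated to benefit. At stake is what the three medication win ratios, and the drug-number and index endpoints, can be said to show.

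**Working it through.** The SAP gives no win-ratio figure, so there is nothing of its own to reproduce. The text check comes first: sections 1.1.2, 2.1 and 2.4 (win ratio), 1.1.3 and 2.7.2 (medication) and 2.8 (adverse events) contain no rule linking the cause of a reduction to the scoring. Two of the three definitions say that any decrease counts.

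The size can only be illustrated. All inputs are assumptions except the 5 and 10 mmHg thresholds:

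- no BP difference between arms; 24-h change mean -4 (SD 12), office change mean -6 (SD 16), correlation 0.4;
- criteria applied in the order listed, with a win being a fall in BP (the SAP states neither);
- other reductions in 10% of each arm; harm-driven reductions in proportion h, independent of the others and of BP.

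**Pairs that reach the medication criterion**

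- *Within-patient cut-offs.* The cut-offs are met with probability 0.467 (24-h) and 0.401 (office). The joint cells are 0.251 (both), 0.216 (24-h only), 0.151 (office only) and 0.383 (neither). A pair ties on BP when both patients fall in the same cell: t = 0.251² + 0.216² + 0.151² + 0.383² = 0.279.
- *Between-patient margins.* Differences between two patients have SD 12√2 = 17.0 and 16√2 = 22.6, correlation 0.4. The probability that both lie within 5 and 10 mmHg is t = 0.086.

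**Win ratio**

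WR = [(1-t)/2 + t·dR(1-dS)] / [(1-t)/2 + t·dS(1-dR)], where dR and dS are the proportions credited with a reduction in the RDN and sham arms.

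As written, d = 1 - 0.90(1-h). For h = 15% and 5%:

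- dR = 1 - 0.90 × 0.85 = 0.235; dS = 1 - 0.90 × 0.95 = 0.145.
- dR(1-dS) = 0.2009 and dS(1-dR) = 0.1109, a ratio of 1.81 within BP-tied pairs.
- Cut-offs: (0.3605 + 0.279 × 0.2009)/(0.3605 + 0.279 × 0.1109) = 1.06.
- Margins: (0.457 + 0.086 × 0.2009)/(0.457 + 0.086 × 0.1109) = 1.02.

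If a patient with a harm-driven reduction earns no medication win, d = 0.10(1-h), so dR = 0.085 and dS = 0.095. The ratios become 0.99 (cut-offs) and 1.00 (margins).

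| Harm-driven, RDN vs sham | Cut-offs: as written / not credited | Margins: as written / not credited |
|---|---|---|
| 5% vs 5% | 1.00 / 1.00 | 1.00 / 1.00 |
| 15% vs 5% | 1.06 / 0.99 | 1.02 / 1.00 |
| 20% vs 5% | 1.10 / 0.99 | 1.02 / 1.00 |
| 5% vs 15% | 0.94 / 1.01 | 0.98 / 1.00 |

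**Sensitivity to the BP assumptions.** A simulation with mean changes of zero and correlation 0.5 sends about 37% of pairs (cut-offs) or 9% (margins) to the medication criterion. For 15% vs 5%, 25% vs 5% and 30% vs 0% it gives 1.10, 1.19 and 1.30 under cut-offs, and 1.02, 1.04 and 1.05 under margins.

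**If withdrawal raises BP.** Suppose a harm-driven withdrawal raises 24-h and office systolic BP by 5 and 6.7 mmHg. For 15% vs 5% the ratio as written is then about 1.01 to 1.02 (cut-offs) and 0.96 to 0.97 (margins). At 8 and 10.6 mmHg it is 0.99 and 0.93. Under the first set of assumptions, with or without these BP rises, crediting the harm-driven reductions raised the ratio for the arm with more of them each time, by about 0.02 to 0.12 for 15% or 20% vs 5%.

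**The case against.** A reader might infer that the win ratio points the wrong way exactly when the device does harm. The documents do not support that. They give no withdrawal rates and nothing that places more harm-driven reductions in the RDN arm. The scoring is symmetric, so more withdrawals under sham would count against the device. A withdrawn antihypertensive may also raise BP and lose the patient the BP criteria that are listed first, which can hold the overall ratio at or below 1.

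Nor is the harm hidden. Adverse events of special interest and renal function are compared by arm under section 1.1.5, and the BP-only win ratio shows whether a result depends on the medication criterion. Section 2.4 makes all these analyses exploratory. Sampling error is also far larger: under the cut-off assumptions the central 95% of simulated win ratios runs from about 0.57 to 2.01 with 40 per arm, and recruitment stopped short of the planned 80 patients.

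Two further objections have force. Treating every reduction linked to an adverse event as no win could remove real benefit, because a drug cut for low BP may reflect the intended effect. And the SAP names no field for the reason of a medication change. Rules on medication changes may also sit in the protocol, which is not shown, but the SAP sets the scoring of a win and cites no such rule.

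These points limit the size of the problem and shape the remedy. They do not remove the scoring flaw: the BP-only version does not correct the other three, and reporting a harm as a safety event does not stop it from also being credited as efficacy.

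**Conclusion.** The point holds for three of the four win ratios, at the medication criterion, and in the same way for the change in drug number and indices. Creatinine rise, eGFR fall and high potassium carry it; hypotension does not, because it may be true BP lowering. For 15% against 5% harm-driven reductions and no BP effect, the shift is about 0.07 on the win ratio under cut-offs and about 0.02 under margins. The SAP does not say which of the two it means, or that the criteria form a strict order. The rates, the SDs and the independence of withdrawal from BP are all assumed. An overall reversal of the result is not shown. What changes is interpretation: as planned, a medication win cannot be read as reduced need for treatment without knowing why the drug was reduced.

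**What to change.** Before unblinding:

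1. At the Blinded Data Review Meeting (section 2.6), classify the reason for each reduction blind to arm, using the entry "Action taken /treatment" on the adverse event form (section 2.8) and the medication-change records (section 2.7.2).
2. Keep the planned scoring. Add a pre-specified version of the three medication win ratios, and of the change in drug number and indices, in which reductions made for renal or potassium adverse findings earn no win and no credit.
3. Treat hypotension-driven and unclear reductions as a separate sensitivity category.
4. Report reductions driven by adverse events by arm with the safety results.

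The cost is a few lines of SAP text, a blinded review limited to patients with a reduction, and one extra run per analysis. Some reasons will stay unclear, which the third step accommodates. The change concerns scoring only, not clinical management.

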- Change in number of antihypertensive drugs at 3, 6 and 12 months post-procedure from pre-procedure (pre-procedure visit (week -1)) compared between the 2 groups.
- Change in drug burden index at 3, 6 and 12 months post-procedure compared from pre-procedure (pre-procedure visit (week -1)) between the 2 groups (RDN-Treatment group vs. Sham group).
- Change in antihypertensive load index at 3, 6 and 12 months post-procedure from pre-procedure (pre-procedure visit (week -1)) compared between the 2 groups (RDN-Treatment group vs. Sham group).
- Percentage of subjects requiring initiation of additional antihypertensive drug therapy between 3 and 6 months post-procedure compared between the 2 groups (RDN-Treatment group vs. Sham group).
- Change in following body fluid composition parameters measured by the Body Composition Monitor (BCM), Fresenius Medical Care at 3, 6 and 12 months post-procedure from pre-procedure (pre-procedure visit (week -1)) compared between the 2 groups (RDN-Treatment group vs. Sham group)
 - o Weight, height, BMI, Overhydration (OH), OH % of extra cellular water
- Change in following parameters at all ambulatory BP measurements (24 hours ambulatory values, ambulatory values- day time and ambulatory values- night time) derived from Mobilograph® examination at 3, 6 and 12 months post-procedure from (pre-procedure visit (week -1)) compared between the 2 groups (RDN-Treatment group vs. Sham group).
 - o Pulse pressure, central systolic pressure (zSys), central diastolic pressure (zDia), augmentation index at 75 beats per minute (AIx at 75 bpm), heart minute volume (HMV), peripheral resistance, reflexion coefficient, pulse wave velocity (PWV)

All the analyses with respect to the 24 hour ambulatory parameters or office blood pressure parameters described under 1.1.1, 1.1.2 and 1.1.3 will be performed by comparing the treatment values at 3, 6, and 12 months from the pre-procedure value (1. Pre-treatment value (**P**) = average of the pre-procedure visit (week -1) value and screening visit (week - 4) value, 2. Baseline value (**B**) = pre-procedure visit (week -1) value only) in the RDN group and the sham group, separately (paired analyses) and compared *between the 2 groups*.

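### The medication win ratios take a decrease from P as well as B, while the SAP's own medication endpoints use week -1 only, so the P version can count run-in drug changes as post-procedure decreases

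*SAP*

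**What the plan says.** SAP 1.1.1 defines two pre-procedure references. P is the "average of the pre-procedure visit (week -1) value and screening visit (week -4) value". B is the "pre-procedure visit (week -1) value only) compared" between the groups.

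SAP 1.1.2 lists, among the secondary objectives, three win ratios that combine ambulatory systolic BP, office systolic BP and one medication measure. The medication parts read:

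- drug number: "decrease of medication number at 3, 6 and 12 months from pre-procedure (including P and B")
- drug burden index: "any decrease of drug burden index in both groups at 3, 6 and 12 months from pre-procedure (including P and B) in both groups"
- antihypertensive load index: "any decrease of antihypertensive load index at 3, 6 and 12 months from pre-procedure (including P and B")

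SAP 2.1 repeats all three, for example "any decrease of drug burden index in both groups at 3, 6 and 12 months from pre-procedure (including P and B"). SAP 2.4 names the three medication measures again, without a reference value.

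The same quantities are also endpoints in their own right, and there the reference is week -1 alone. SAP 1.1.3 has "Change in number of antihypertensive drugs at 3, 6 and 12 months post-procedure from pre-procedure (pre-procedure visit (week -1")) and "Change in drug burden index at 3, 6 and 12 months post-procedure compared from pre-procedure (pre-procedure visit (week -1")), with matching wording for the load index, and 2.1 agrees. The closing paragraph of 1.1.3, which sets the P and B rule for 1.1.1 to 1.1.3, names ambulatory and office blood pressure parameters and does not name medication.

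**The concern.** One document gives one quantity two reference values. Averaging two readings makes sense for blood pressure, where it reduces measurement noise. A regimen has no comparable noise: if it differs between week -4 and week -1, the mean describes a regimen the patient may never have taken, and the difference arose before randomisation.

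If the win-ratio wording is followed as written, the P version can credit a run-in change to the period after the procedure and can miss a real later reduction. The medication part of the win ratio would then disagree with the stand-alone medication endpoint for the same patient. A programmer could in good faith follow either reading.

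**Working it through.** The SAP gives no win-ratio figure to reproduce. The check applies its definitions and then illustrates the effect with assumed rates.

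**Step 1: can P be computed for medication, and does it precede randomisation?** The flow sheet in 1.3 marks a medication review at V1 (week -4) and V2 (week -1). Section 1.2 places randomisation after the diagnostic angiogram, and the flow sheet puts the procedure at week 0. So P is computable, and both of its parts are pre-randomisation values.

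**Step 2: when do P and B disagree?** Let W4, W1 and F be the values at week -4, week -1 and follow-up. A decrease under P means F < (W4 + W1)/2. A decrease under B means F < W1.

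| W4 / W1 / F | P | F - P | Decrease under P | F - B | Decrease under B |
|---|---|---|---|---|---|
| 4 / 3 / 3 | 3.5 | -0.5 | yes | 0 | no |
| 5 / 4 / 4 | 4.5 | -0.5 | yes | 0 | no |
| 3 / 5 / 4 | 4.0 | 0 | no | -1 | yes |
| 3 / 4 / 3 | 3.5 | -0.5 | yes | -1 | yes |
| 4 / 4 / 3 | 4.0 | -1.0 | yes | -1 | yes |

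One drug stopped between week -4 and week -1 and not resumed is enough to create a decrease under P. Missing a real decrease in a whole-number count takes more. F must be at least one below W1 yet not below the mean, so W1 - W4 must be at least 2, as in the third row. With one drug added and then removed (fourth row), the two references agree.

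**Step 3: illustration of dilution.** Consider the medication criterion alone. Let p1 and p0 be the proportions with a true post-procedure decrease in RDN and sham. Then

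win ratio = p1(1 - p0) / [p0(1 - p1)].

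Suppose a proportion r in both arms stops a drug between weeks -4 and -1 and does not resume it, independently of later changes, and nobody adds one. Under P each p becomes p + (1 - p)r. All of these rates are assumptions; the SAP gives none.

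With p1 = 0.20 and p0 = 0.08:

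- r = 0: 0.20 × 0.92 / (0.08 × 0.80) = 2.88
- r = 0.05: 0.24 × 0.874 / (0.126 × 0.76) = 2.19
- r = 0.10: 0.28 × 0.828 / (0.172 × 0.72) = 1.87
- r = 0.20: 0.36 × 0.736 / (0.264 × 0.64) = 1.57

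With p1 = 0.20 and p0 = 0.10:

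- r = 0: 0.20 × 0.90 / (0.10 × 0.80) = 2.25
- r = 0.05: 0.24 × 0.855 / (0.145 × 0.76) = 1.86
- r = 0.10: 0.28 × 0.81 / (0.19 × 0.72) = 1.66
- r = 0.20: 0.36 × 0.72 / (0.28 × 0.64) = 1.45

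If p1 = p0, the ratio stays at 1.00 for every r.

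**Step 4: chance imbalance.** Section 2.4 gives 20 randomised patients for the Erlangen and Nürnberg cohort. If they split 10 and 10 (an assumption), one misclassified patient enters 10 of the 100 pairwise comparisons.

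**The case against.** The best defence is that the SAP already means the right thing. P is introduced for blood pressure, the closing rule of 1.1.3 attaches P and B to ambulatory and office blood pressure, and each medication win ratio contains two blood pressure criteria to which the parenthesis could belong. That reading is plausible and may well be the intention. It is not what the bullets say: for drug number and the load index the parenthesis directly follows the medication criterion and its time points, and the drug burden bullet is built the same way. Section 2.4 gives no reference, so it does not settle the matter.

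The remaining objections stand and limit the point.

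- A reader might infer that any drug stopped before randomisation becomes a win. It does not. Only the P version is affected, the stop must fall between weeks -4 and -1, and it must persist. Meeting the criterion gives a win only against a patient without a decrease. A stop between week -1 and the procedure counts under B as well, and the fix does not change that.
- A reader might infer a bias towards RDN. Both reference visits precede randomisation, so run-in changes are expected to be equal in the two arms.
- A reader might infer that the medication criterion decides every pair tied on blood pressure. The SAP lists the criteria but states no ranking and no tie rule, so the weight of this criterion in the full win ratio is unknown.
- The word any is written only for the two indices. For drug number the text says decrease and sets no minimum, so half a drug qualifies by plain reading, not by an explicit rule.
- Nothing in the SAP shows that drugs were stopped in the run-in. If regimens were stable, P equals B for medication and the effect is nil.
- The B version is already planned alongside P, and 2.4 describes the whole analysis as exploratory and descriptive.

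**Conclusion.** The inconsistency is in the text, and the arithmetic shows that it can change a patient's classification. It is limited to the P version of three secondary, exploratory win ratios; the primary analysis is untouched. The expected consequence is attenuation of a real medication effect, plus added chance imbalance in a trial that did not reach its target of 80.

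The size cannot be stated from the SAP. The illustrative falls, to between 2.19 and 1.57 from 2.88 or to between 1.86 and 1.45 from 2.25, rest on assumed decrease rates and on run-in stop rates of 5% to 20%. They also assume that every stop persists and that no drugs are added, and they describe the medication criterion alone. The change in the reported win ratio would further depend on the unstated tie rules. A correction is worth making because the SAP's own endpoints already supply the consistent reference.

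**What to change.** In SAP 1.1.2 and 2.1, reword the three medication win ratios, and add the same statement to 2.4: P and B apply to the ambulatory and office blood pressure criteria only; a decrease in drug number, drug burden index or antihypertensive load index is measured from the week -1 value in both the P and the B version, as in 1.1.3.

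The cost is one sentence, placed consistently in three sections. Week -1 medication is already collected, so no new data are needed, and the B version is unchanged.
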